12.4.8.1. Adverse Events

Treatment-emergent AEs and non-TEAEs (those occurring prior to administration of study medication or that first occurred prior to study drug administration and did not worsen in frequency or severity) will be listed. TEAEs will be defined as AEs that occur on or after the date and time of study drug administration, or those that first occur pre-dose but worsen in frequency or severity after study drug administration. AEs will be followed-up until complete resolution, or until the PI or Sub-Investigator judges safe to discontinue follow-up.

The incidence of TEAEs will be summarized using the safety population. The MedDRA® dictionary Version 23 will be used to classify all AEs reported during the study by system organ class (SOC) and preferred term (PT). Incidence of subjects who experienced TEAEs will be presented by treatment and overall, SOC, PT, by Investigator-assessed relationship and also by severity. Each subject may only contribute once to each of the incidence rates, for a TEAE following a given treatment, regardless of the number of occurrences; the highest severity or highest relationship will be presented, as appropriate. In each table, SOC will be presented in descending order of overall incidence rate in terms of frequency of subjects and then in frequency of events (alphabetical order will be used in case of equal rates). For each SOC, PT will be presented the same way.

Incidence of TEAEs (number of events) will also be presented by treatment and overall, by SOC, and PT, by Investigator-assessed relationship and severity.

Severity of AEs will be rated according to CTCAE criteria as outlined in Section 9.4 and defined in Table 3 as Grade 1 (mild), Grade 2 (moderate), Grade 3 (severe), Grade 4 (life-threatening) and Grade 5 (fatal).

12.4.8.2. Laboratory Parameters

Clinical laboratory tests including biochemistry, hematology, and other screening tests, will be performed as listed in Table 6, and at time points specified in the SoA (Table 1). Microscopic examination will be performed on abnormal findings. Listings of all clinical laboratory results will be provided with the abnormal values flagged with "L" (Below normal range) and "H" (Above normal range) for continuous parameters, and "N" (Normal Range) for categorical parameters.

Descriptive statistics (mean, median, SD, Min, Max, and sample size) for each clinical laboratory test (continuous variables) will be presented. Change from baseline to study exit will also be presented. For a given laboratory test, any value (scheduled or unscheduled), prior to the first dosing will replace any missing screening value (if scheduled value is missing). However, unscheduled results will not be included in the summary tables. For categorical variable, the number of subjects (frequency and percentage) will be tabulated by results (e.g., negative, positive, trace, etc.). A summary table of shifts from screening to study exit will be provided.

Results from repeat tests will not be included in the summary statistics unless the repeat was required (and documented as such) due to technical reasons or an invalid initial result.

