r.	COVID-19 symptoms will be documented by the patient on the applicable diary every day and reviewed by the study staff on Day 1, Day 4, Day 6, Day 8, Day 11, Day 22, Day 28. Patients should be instructed to collect this data on their patient diary every day, at the same time they take their study drug, until study completion. Patients should be instructed to return the paper diary to each clinic visit for review by study personnel. A copy of the paper diary will be collected as part of the source documentation and the original returned to the subject until the next visit. The original diary will be collected at the day 28 visit. Sites should schedule all visits, including phone visits, as close as possible to the drug dosing time on Day 1 to ensure consistency when reviewing patient symptoms.
s.	Serum or urine pregnancy testing will be performed in women of childbearing potential only. Pregnancy testing should be performed at Screening.
t.	Blood for genomic DNA and RNA will be used to assess for polymorphisms in the patient and the virus that may affect safety or efficacy; to be collected at Screening.
u.	Nasopharyngeal swabs collection to determine SARS-CoV-2 viral load and possibly sequence, expression biomarkers of target engagement and infectious disease diagnostic (Biofire or equivalent) to be collected on Day 1 (immediately prior to the first dose) and then on Day 4. The Day 4 swab should be obtained as close to 72 hours (\pm 4 hours) after the Day 1 dose as possible.
v.	Saliva collection to determine SARS-CoV-2 viral load, and possibly sequence and expression biomarkers of target engagement to be collected on Day 1 (immediately prior to the first dose) and then on Day 4, Day 11, and Day 28. NOTE: The Day 4 sample should be obtained as close to 72 hours (\pm 4 hours) after the Day 1 dose as possible.
w.	Hematology to include hemoglobin, hematocrit, erythrocyte count, absolute counts of leukocytes, neutrophils, lymphocytes, monocytes, eosinophils, basophils; platelet count. Hematology testing should be performed on Day 1 (predose), and Day 11. NOTE: Hematology results obtained within 30 days prior to the Screening visit are acceptable for the Day 1 sampling requirement.

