9. SAFETY ASSESSMENT

9.1. Definitions

9.1.1. Adverse Event

An AE is any untoward medical occurrence in a clinical investigation subject administered a medicinal product; the event does not necessarily have a causal relationship with study drug administration or usage. An AE can therefore be any unfavorable and unintended sign (including an abnormal laboratory finding), symptom, or disease temporally associated with the use of a medicinal product, whether or not considered related to the medicinal product.

In this study, any of the following events will be considered an AE:

- Any complication that occurs as a result of a protocol-mandated procedure (e.g. venipuncture, ECG).
- Any preexisting condition that increases in severity or changes in nature during or as a consequence of study drug administration. Worsening manifestations of the underlying infection (e.g. increase in COVID-19 manifestations) may be considered AEs in this study.
- Any injury or accident. If a medical condition is known to have caused the injury or accident (e.g. a fall secondary to dizziness), the medical condition (dizziness) and the accident (fall) should be reported as 2 separate AEs.
- Any abnormality in physiological testing or a physical examination finding that requires clinical intervention or further investigation (beyond ordering a repeat [confirmatory] test).
- Any laboratory (e.g. clinical chemistry, hematology, urinalysis) or investigational abnormality (e.g. ECG, X-ray) independent of the underlying medical condition that requires clinical intervention, results in further investigation (beyond ordering a repeat [confirmatory] test), or leads to investigational medicinal product interruption or discontinuation unless it is associated with an already reported clinical event. If the laboratory abnormality is part of a syndrome, the syndrome or diagnosis (e.g. anemia) not the laboratory result (e.g. decreased hemoglobin) should be recorded.
- A complication related to pregnancy or termination of a pregnancy (see Section 9.7.2 for additional information).

None of the following events is considered an AE:

- Laboratory abnormalities not requiring clinical intervention or further investigation. Such abnormalities will be captured as part of laboratory monitoring.

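### Laboratory summaries omit unscheduled results and non-technical repeats and run to an undefined 'study exit', so some post-dose abnormalities not reported as AEs reach only the listings

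*Combined protocol and SAP*

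**What the plan says.** Section 12.4.8.2 (Laboratory Parameters) sets these rules:

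- **Unscheduled results:** "However, unscheduled results will not be included in the summary tables". At baseline there is one allowance: "any value (scheduled or unscheduled), prior to the first dosing will replace any missing screening value".
- **Repeat tests:** these stay out of the summary statistics "unless the repeat was required (and documented as such) due to technical reasons or an invalid initial result".
- **Change:** "Change from baseline to study exit will also be presented".
- **Shift:** "A summary table of shifts from screening to study exit will be provided".
- **Listings:** "Listings of all clinical laboratory results will be provided with the abnormal values flagged", using low, high and normal flags.

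The section names no worst post-baseline or CTCAE-graded laboratory table.

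For timing, Table 1 footnote w says: "Hematology testing should be performed on Day 1 (predose), and Day 11". Footnote x gives the same two days for chemistry. The Table 1 grid marks both tests at Screening, Day 11 and Early Termination.

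Section 9.1.1 lists among events that are not AEs: "Laboratory abnormalities not requiring clinical intervention or further investigation. Such abnormalities will be captured as part of laboratory monitoring".

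**The concern.** Sections 9.1.1 and 12.4.8.2 each lean on the other. The AE definition passes lesser laboratory abnormalities to laboratory monitoring. The laboratory summaries then drop those that came from an unscheduled draw or an ordinary repeat. A value that falls between the two sections is never compared between arms in a table.

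The schedule makes this matter more than usual, because a subject who completes has only one scheduled post-dose safety sample. Extra draws are therefore the only laboratory information on the rest of the 28 days. Safety and tolerability is a secondary objective (section 3.2.1), and section 12.4.8 names hepatobiliary and blood disorders among the outcomes described by arm.

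Separately, 'study exit' has no clear meaning for laboratory data, so a programmer would have to guess which value to use.

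**Working it through.** No plan figure is involved, so the check sets the sections side by side.

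**1. Scheduled post-dose safety blood (Table 1, footnotes w and x).**

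| Visit | Hematology and chemistry |
|---|---|
| Day 4 | none |
| Days 6 and 8 (telephone) | none |
| Day 11 | yes |
| Day 22 (telephone) | none |
| Day 28 | none |
| Early Termination | yes |

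A completer has 1 scheduled post-dose draw across 6 follow-up visits.

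**2. What 'study exit' can mean.** Section 8.6 runs follow-up through Day 28, but no safety blood is scheduled then. For laboratory data the term can only point to the Day 11 or Early Termination value. The text does not say so, and it does not say which applies if a subject has both.

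**3. Which post-dose results reach a by-arm laboratory table (section 12.4.8.2).**

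| Result | Summary or shift table | Listing |
|---|---|---|
| Scheduled Day 11 or Early Termination value | yes | yes |
| Repeat for a technical reason or invalid first result | yes | yes |
| Other repeat | no | yes |
| Unscheduled post-dose result | no | yes, if recorded |

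The qualifier in the last row comes from the Study Activities part of the synopsis, which says additional laboratory data are not necessarily collected unless Table 1 specifies them.

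**4. Which of the excluded results reach an AE table instead.** Under section 9.1.1 a laboratory abnormality is an AE if it needs intervention, prompts investigation beyond a confirmatory repeat, or leads to interruption or discontinuation of study drug. It does not matter which draw found it. From first dose to Day 28 it is then a TEAE (section 9.1.4), tabulated by arm, system organ class, preferred term and highest severity (section 12.4.8.1).

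That criterion has limits. It covers abnormalities independent of the underlying condition, leaves out those tied to an already reported clinical event, and records the diagnosis rather than the laboratory value when the abnormality is part of a syndrome.

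**5. What is left.** These are post-dose abnormalities found only on an unscheduled draw, or only on a non-technical repeat, and not reported as AEs. They appear in listings at most.

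The protocol itself provides a route to such results. Section 8.1.8 allows more frequent safety laboratory tests after an overdose, and section 9.1.1 says an overdose without clinical sequelae is not an AE.

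**The case against.** The case against is substantial, and most of it stands.

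- **AE tables.** A reader might infer that a laboratory toxicity absent on Day 11 vanishes from the safety tables, or that transient on-drug abnormalities cannot differ between arms in any table. The documents do not support this. An abnormality that meets the section 9.1.1 definition is tabulated by arm as a TEAE. Section 12.4.8 also describes Grade 3 and 4 AEs and hepatobiliary and blood disorders by arm. The exclusion governs laboratory summaries only.
- **Repeats.** The repeat rule often protects the signal, because an abnormal scheduled Day 11 value stays in the table even if a later repeat is normal. It loses information only when the repeat is worse than the first result.
- **Listings.** Recorded results are kept and flagged. This stands, but a line listing for about 142 subjects does not compare arms.
- **Size.** A reader might put a number on the loss from the chance that an episode of k days covers Day 11. If onset is assumed uniform over Days 2 to 28, that chance is k/27: 3/27 = 11%, 7/27 = 26% and 10/27 = 37%. If onset is assumed uniform over Days 2 to 11, close to the dosing period, it is k/10: 30%, 70% and 100%. Neither set measures this gap. Both describe overlap with the visit schedule. An episode that misses Day 11 and has no extra draw is never seen, so no table rule could recover it. The documents give no rate of unscheduled draws.
- **Deferral.** Section 12 leaves full methods to a SAP filed before database lock. A SAP could add a table, but that does not cancel an exclusion stated explicitly in section 12.4.8.2.
- **Collection.** Extra results may be incomplete, and they are drawn for cause. This stands and shapes the fix.

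**Conclusion.** The point holds in a narrow form. Section 12.4.8.2 leaves 'study exit' undefined for laboratory data. It also keeps post-dose unscheduled results and non-technical repeats out of the by-arm laboratory summaries, with no worst-value table to offset this. Abnormalities seen only on such results and not reported as AEs reach listings at most, although section 9.1.1 relies on laboratory monitoring to capture them.

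The severity is minor. Abnormalities meeting the AE definition are tabulated elsewhere, and the number of results in the gap cannot be estimated from the documents. The conclusion assumes that section 12.4.8.2 is applied as written and that Table 1 is the full laboratory schedule. Limiting means to scheduled values is a sound choice and is not criticised.

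**What to change.** In section 12.4.8.2, and in the SAP:

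1. Define 'study exit' for laboratory data as the Day 11 or Early Termination value, and say which is used if a subject has both. Keep means and mean change on scheduled values.
2. Add one by-arm shift table from baseline to worst post-baseline CTCAE grade, using all recorded post-dose results: scheduled, unscheduled, repeat and Early Termination.
3. State that post-dose unscheduled safety results, when obtained, are entered in the eCRF, and align the Study Activities wording in the synopsis with this.

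The cost is a wording change, one table program and some extra data entry at sites. No visit, sample or primary analysis changes. The downside is that for-cause sampling is informative and may be incomplete, so these values should enter only the worst-grade table, with a footnote saying so.

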12.4.9. Other Safety Analyses

Any other safety analysis will be made on the safety population.

12.5. Interim Analyses

The study will incorporate an interim analysis for safety after the first 30 subjects (15 on LAM-002A and 15 on placebo) have completed treatment and have been followed up to Day 11. Recommendations from an independent Data Safety Monitoring Board (DSMB) will be used for decision of early termination or design adaptations (see table of Death Trigger Study Termination below). No formal assessment of futility or efficacy will be performed at this first interim report.

Subsequent interim DSMB reports will be reviewed with no more than 6 months between reviews. In addition to safety, at 50% enrollment the DSMB will review the proportion of participants that have a baseline viral load of $>10^5$ copies/ml. Based on this proportion the DSMB may recommend an increase in sample size to assure a sufficient number of participants in the subgroup for primary analysis. If a recommendation for a sample size increase is being considered, futility will be examined via conditional power to assist in this determination. Details will be provided in the SAP.

The first interim analysis for safety will be conducted and presented to the DSMB when 15 participants in each treatment arm have reached 11 days following randomization. At this review, it is proposed that the study be stopped if mortality is significantly higher in the LAM-002A arm compared to placebo arm based on a Fisher's exact test. Table 8 shows the differences in deaths between the LAM-002A and placebo arm that will prompt discontinuation of the study.

Placebo Deaths, n	LAM-002A Deaths, n	Difference (LAM-002A – Placebo)	Fisher's Exact P-Value
0	5	5	0.042
1	7	6	0.035
2	8	6	0.05
3	10	7	0.025
4	11	7	0.027
5	12	7	0.025
6	13	7	0.021
7	13	6	0.050

Table 8.Death Boundary for Study Termination

13. STUDY ADMINISTRATION AND RESPONSIBILTIES

13.1. General Investigator Responsibilities

The principal investigator must ensure that:

- He or she will personally conduct or supervise the study.
- His or her staff and all persons who assist in the conduct of the study clearly understand their responsibilities and have their names included in the relevant Study Personnel documents.
- The study is conducted according to the protocol and all applicable regulations.
- The protection of each subject's rights and welfare is maintained.
- Signed and dated informed consent and, when applicable, permission to use protected health information are obtained from each subject before conducting study procedures. If a subject withdraws permission to use protected health information, the investigator will obtain a written request from the subject and will ensure that no further data be collected from the subject.
- The consent process is conducted in compliance with all applicable regulations and privacy acts.
- The IRB/IEC complies with applicable regulations and conducts initial and ongoing reviews and approvals of the study.
- Any amendment to the protocol is submitted promptly to the IRB/IEC.
- Any significant protocol deviations are reported to the medical monitor, the sponsor, and the IRB/IEC according to the guidelines at each study center.
- eCRF pages are completed in a timely fashion.
- All SAEs are reported to the sponsor (or designee) within 24 hours of knowledge and to the IRB/IEC per IRB/IEC requirements.
- All safety reports are submitted promptly to the IRB/IEC.

13.2. Protocol Compliance

The investigator is responsible for ensuring the study is conducted in accordance with the procedures and evaluations described in this protocol.

13.3. Compliance with Ethical and Regulatory Guidelines

The investigator will ensure that this study is conducted in accordance with ICH guidelines, or with the laws and regulations of the country in which the research is conducted, whichever affords the greater protection to the study subject. For studies conducted under a US IND, the investigator will ensure adherence to the basic principles of GCP as outlined in 21 CFR 312, subpart D, "Responsibilities of Sponsors and Investigators," 21 CFR, Part 50, 1998, and 21 CFR, Part 56, 1998.

This study is also subject to and will be conducted in accordance with 21 CFR, Part 320, 1993, "Retention of Bioavailability and Bioequivalence Testing Samples." Because this is a "covered" clinical trial, the investigator will ensure adherence to 21 CFR, Part 54, 1998; a covered clinical trial is any "study of a drug or device in humans submitted in a marketing application or reclassification petition subject to this part that the applicant or FDA relies on to establish that the product is effective (including studies that show equivalence to an effective product) or that make a significant contribution to the demonstration of safety." This requires that investigators and all sub-investigators must provide documentation of their financial interest or arrangements with the sponsor, or proprietary interests in the drug being studied. This documentation must be provided before participation of the investigator and any sub-investigator in the trial. The investigator or sub-investigator agrees to notify the sponsor of any change in reportable financial interests during the study and for 1 year following completion of the study. Study completion is defined as the date that the last subject has completed the protocol-defined activities.

13.4. Institutional Review Board/Independent Ethics Committee (IRB/IEC)

This protocol and any accompanying material to be provided to the subject (such as advertisements, subject information sheets, or descriptions of the study used to obtain informed consent) will be submitted by the investigator to an IRB/IEC. Approval from the IRB/IEC must be obtained before starting the study and should be documented in a letter from the IRB/IEC to the investigator specifying the protocol number, protocol version, protocol date, documents reviewed, and date on which the committee met and granted the approval. A signed protocol approval page, a letter confirming IRB/IEC approval of the protocol and informed consent, and a statement that the IRB/IEC is organized and operates according to GCP and the applicable laws and regulations must be forwarded to the sponsor before screening subjects for the study. Additionally, study centers must forward a signed Form FDA 1572 (Investigator Obligation Form) to the sponsor before screening subjects for study enrollment.

Any modifications or amendments made to the protocol or informed consent document after receipt of the initial IRB/IEC approval must also be submitted to the IRB/IEC for approval before implementation. Only changes necessary to eliminate apparent immediate hazards to the subjects may be initiated prior to IRB/IEC approval. In that event, the investigator must notify the IRB/IEC, the medical monitor, and the sponsor in writing within 5 working days after implementation. If a change to the protocol in any way increases the risk to the subject or changes the scope of the study, then written documentation of IRB/IEC approval must be received by the sponsor before the amendment may take effect. Additionally, under this circumstance, information on the increased risk and/or change in scope must be provided to subjects already actively participating in the study, and they must read, understand, and sign any revised informed consent document confirming willingness to remain in the trial.

The investigator shall submit a progress report at least once yearly to the IRB/IEC and must provide a copy to the sponsor. As soon as possible after completion or termination of the study, the investigator will submit a final report to the IRB/IEC and to the sponsor. This report should include the dates of initiation and completion of the trial, a description of any changes in study procedures or amendments to the protocol, any deviations from the protocol, the number and type of subjects evaluated, the number of subjects who discontinued (and the reasons for discontinuation), the number of subjects who completed the trial, and the results of the trial, including a description of any AEs. The sponsor will assist the investigator in the preparation of this report, as needed.

